## **Measures and Participant Assessments**

*Diagnostic/Screening:* Age, demographics, race, education, current treatments and psychopharmacologic medication history will be recorded. SCID-5 - The Structured Clinical Interview for DSM-5 (First, 2014) will be used to establish psychiatric diagnoses, current and lifetime, and inclusion/exclusion criteria.

PTSD: CAPS-5 – The Clinician Administered PTSD Scale (Weathers et al., 2013a) will be used to establish a PTSD diagnosis at baseline, and change in scores over time will capture symptom change after TBS and at the end of the follow up period. PCL-5 – The PTSD Checklist (Weathers et al., 2013b) is a 20-item self-report scale of PTSD symptoms. LEC-5 – The Life Event Checklist (Weathers et al., 2013c) assesses for lifetime trauma exposure.

Mood, Affect and Anxiety: IDS-SR – the Inventory of Depressive Symptoms, Self Report (Rush et al., 2003) is a self-report scale that provides a continuous measure of depression severity. PANAS – The Positive and Negative Affect Schedule (Watson et al., 1988) will evaluate changes in affective status. STAI – The State-Trait Anxiety Scale (Spielberger et al., 1983) will evaluate changes in anxiety outside of PTSD symptoms. Quality of Life, Function and Sleep: QLESQ-SF – The 18-item Quality of Life Enjoyment and Satisfaction Questionnaire (Ritsner et al., 2005) evaluate QOL and other areas of change related to functioning outside of symptom domains. SOFAS – The Social and Occupational Functioning Scale (Morosini et al., 2000) will evaluate changes in functional status attributable to study procedures. PSQI – The Pittsburgh Sleep Quality Index (Buysse et al., 1989) will assess changes in quality of sleep.

*General:* CGI – The clinical global impressions of severity and improvement (Guy, 1978) will be used to capture overall symptom severity and improvement associated with treatment.

Treatment Satisfaction – The treatment satisfaction form (Blatt et al., 1998) will gather feedback from participants related to study participation.

*Blinding*: At double blind endpoint Veterans will be queried as to whether they received active or sham.

## DATA ANALYSIS

**Feasibility and Acceptability.** Feasibility will be evaluated by rates of recruitment, treatment adherence, retention and completion of assessments. Acceptability will be measured by retention and participant reports of acceptability and satisfaction. To determine the feasibility and acceptability of TBS, we will examine rates of session attendance (as a proxy for adherence to TBS procedures), dropouts, completion of assessments, number and severity of adverse events, qualitative exit interviews and satisfaction ratings. Feasibility and acceptability of the sham control will use the same procedures as well as assessment of the quality of the sham as indicated above. We will consider 75% session attendance and satisfaction rates of 70% participants as the minimum indicator of acceptability, and completion of a minimum of 75% of end of treatment and 1-month follow up assessments to reflect feasibility. Based on prior use of TBS for depression, we expect fewer than 5% of participants to experience an adverse event, and those that do occur will match the known profile of TBS.

**Data Analysis for RCT.** Random assignment of participants with regard to baseline characteristics to TBS and sham groups will be initially assessed. We will include as covariates *a priori* specified variables that are plausibly important for explaining the outcome (i.e., baseline PTSD, depression symptom severity and quality of life) and potentially differentially distributed by random assignment. We will also evaluate the degree to which Veterans report changes in other treatments during the intervention to ensure observed changes are related to TBS. Preliminary data analysis will calculate rates of dropout, distributional properties of dependent and other variables, and differences between those subjects who agree and decline to participate.

We will use generalized linear mixed models (GLMM) for repeated measures as our primary analysis. GLMM has advantages of greater flexibility in handling missing data, modeling effects of time and variance or covariance structures of our repeated measures, and analyzing dependent variables that are not normally distributed (Carbonari et al., 1994). We will test the hypothesis that iTBS results in more rapid improvement in primary outcomes, i.e. decreased CAPS/PCL and increased QLESQ/SOFAS. Next, we will test if participants randomized to iTBS will demonstrate greater change on outcome variables immediately after treatment completion compared to participants randomized to sham. This analysis focuses on end-of-treatment group (iTBS vs. sham) differences only, controlling for baseline differences. Our third objective is to test whether iTBS results in sustained change in primary outcome measures at 1-month follow-up in the iTBS group as compared to the sham group, again net of any baseline differences. Finally, we will test whether (changes in) clinical symptoms relate to (changes in) quality of life/function measures differently after iTBS vs. sham. Secondary outcomes will include evaluation of changes in other variables that are either hypothesized or directly affected by TBS (e.g., depression and sleep, and illness severity and improvement) over time.

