**Theta-Burst Neuromodulation for PTSD (TBS)** ClinicalTrials.gov Identifier: NCT02769312 Version: August 17, 2017

Participants: 55 adult Veterans, ages 18-70 with current PTSD will participate in study procedures.

*Inclusion criteria:* Principle inclusion criteria will be diagnosis of chronic PTSD, meeting DSM-5 criteria. Eligible male and female Veterans will be between ages 18-70, and, if in treatment, symptomatic despite ongoing stable treatment regimens for at least 6 weeks prior to study procedures. Ongoing medications and psychotherapy will be allowed to continue unchanged during the study. Veterans must also be willing and able to comply with all study related procedures and visits, and capable of independently reading and understanding patient information materials and providing informed consent.

*Exclusion criteria:* For safety, participants must meet established screening criteria safety during MRI, which is implemented as a conservative measure given the novel application of TBS in this population, since MRI involves magnetic fields at similar intensity to those emitted from the stimulation coil. These measures require a patient not having the following (unless MRI-safe): Cardiac pacemaker, implanted device (deep brain stimulation) or metal in the brain, cervical spinal cord, or upper thoracic spinal cord. TMS-specific exclusions are pregnancy/lactation, or planning to become pregnant during the study, lifetime history of moderate or severe traumatic brain injury (TBI), current unstable medical conditions, current (or past if appropriate) significant neurological disorder, or lifetime history of a) seizure disorder b) primary or secondary CNS tumors c) stroke or d) cerebral aneurysm. Other exclusions are any primary psychotic disorder, bipolar I disorder, active moderate/severe substance use disorders (within the last month, excluding nicotine/caffeine, assessed with urine drug testing), have active suicidal intent or plan as detected on screening instruments or in the investigative team's judgment is likely to attempt suicide within 6 months, and other conditions or circumstance that, in the opinion of the investigator team, has the potential to prevent study completion and/or to have a confounding effect on outcome assessments.

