## **Procedures and Symptom Measures**

Following eligibility determination, participants will be randomized to either active or sham TBS, using urn randomization (Wei & Lachin, 1988) with PTSD symptom severity, mild TBI, sex, and depression diagnosis (yes/no) as blocking variables.

*Visit Schedule and TBS Procedures.* Veterans will attend 10 TBS/sham sessions, delivered over 10 consecutive business days. Each session will last approximately 10 minutes. 10 unblinded sessions will be offered after the double blind phase. Veterans will return to the PVAMC one month later for a post-treatment follow assessment to durability of changes observed. All stimulation will be performed with a Magstim Super Rapid2+1 stimulator equipped with a double 70mm biphasic figure-of-eight air-cooled coil, available at PVAMC. Following established procedures for TBS (Huang et al., 2005) iTBS "dose" will be determined based on each Veteran's active motor threshold (AMT). AMT will be determined using standard procedures. The stimulator coil will then be placed tangentially to the scalp with the handle pointing posteriorly. Stimulation will be applied over the hand area of the right motor cortex (M1) and localized for each participant based on the optimal position to elicit MEPs in the contralateral FDI.

Once the AMT has been determined, the coil will be placed over the right DLPFC using the Beam Method (Beam et al., 2009), and active TBS will be delivered at 80% of AMT (Li et al., 2014). iTBS parameters will include stimulation of three pulses at 50 Hz, given every 200 ms (5 times per second). Two-second trains of these stimulations will be repeated every 10 seconds for a total of 1800 pulses (delivered over 570 seconds)(Li et al., 2014). Sham procedures will be identical, except will use the Magstim sham coil. Medications and therapy will be held stable to the extent possible during study participation, and changes in treatment during iTBS will be recorded.

*Participant Safety*. Safety will be assessed at every TBS session by recording spontaneously reported adverse events, and participants will be queried daily about potential side effects associated with TBS such as seizure, headache and dizziness. A licensed physician with experience in both neuromodulation and PTSD will be available at all times during study procedures and all participants will be required to wear hearing protection.

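### Adverse events are asked about daily only for effects already associated with TBS, so the recorded mix leans towards the expected profile and that expectation is only weakly tested

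*Combined protocol and SAP*

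**What the plan says.** The Participant Safety paragraph, under Procedures and Symptom Measures, names two routes into the adverse-event record. The first is passive: "Safety will be assessed at every TBS session by recording spontaneously reported adverse events". The second is active but targeted: "participants will be queried daily about potential side effects associated with TBS such as seizure, headache and dizziness". The three named effects are examples, so the full list may be longer, but the query is confined to effects already linked to TBS. No section describes a general question about health.

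The Feasibility and Acceptability paragraph of DATA ANALYSIS then states, on the basis of earlier use of TBS in depression, "we expect fewer than 5% of participants to experience an adverse event, and those that do occur will match the known profile of TBS". It does not list that profile or say how a match would be judged. The same paragraph will examine "number and severity of adverse events, qualitative exit interviews and satisfaction ratings", and adds for the control arm: "Feasibility and acceptability of the sham control will use the same procedures". The thresholds it sets are 75% session attendance, 70% satisfaction, and 75% completion of end-of-treatment and 1-month assessments.

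**The concern.** If one class of event is sought every day and the other is left to be volunteered, the composition of the recorded events reflects the questioning as well as the intervention. The plan makes a statement about exactly that composition. Its expectation is carried over from depression, whereas these participants are Veterans with PTSD who may continue medication and psychotherapy. Events outside the known profile are the evidence on whether the carry-over is sound, and they have the weaker collection route.

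What is at stake is a safety statement in the report. The trial could say that events matched the known profile when part of that agreement came from the prompt list. Using the same procedure under sham keeps the arms comparable but does not recover events that nobody asked about.

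**Working it through.** **The plan's own figure.** The front section gives the sample: "55 adult Veterans, ages 18-70 with current PTSD will participate in study procedures". 5% of 55 is 2.75. 2/55 = 3.6% and 3/55 = 5.5%, so fewer than 5% means at most 2 participants. The documents give no derivation of the 5%, so there is nothing further to reproduce.

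**Assumptions.** The documents give no detection rates. Everything below is illustrative:
- *t*, the true share of events that are known effects: 50% or 70%
- *p*, detection of a prompted event: 0.9
- *v*, detection of an unprompted event by spontaneous report: 0.9 (equal ascertainment) down to 0.1

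**Step 1: recorded share of known effects.** The formula is k = t·p / [t·p + (1 − t)·v]. For t = 0.7 and v = 0.3, k = 0.63 / (0.63 + 0.09) = 0.875.

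| v | k if t = 50% | k if t = 70% |
|---|---|---|
| 0.9 | 50% | 70% |
| 0.6 | 60% | 78% |
| 0.3 | 75% | 88% |
| 0.1 | 90% | 95% |

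Whenever v is below p, the recorded known share exceeds the true one. The excess runs from nothing to large.

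**Step 2: chance that an unlisted kind of event leaves no trace.** Suppose 5% of participants truly have such an event. The chance that none is recorded among n participants is (1 − 0.05·v)^n. The single-arm column takes n = 28, assuming 1:1 allocation.

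| v | n = 55 | n = 28 |
|---|---|---|
| 0.9 | 0.079 | 0.275 |
| 0.6 | 0.187 | 0.426 |
| 0.3 | 0.436 | 0.655 |
| 0.1 | 0.759 | 0.869 |

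**Step 3: can the expectation still be contradicted?** With m independent recorded events, the chance that at least one is off-profile is 1 − k^m. Take t = 70%:
- For m = 10 (assumed): 1 − 0.700^10 = 97% under equal ascertainment, 1 − 0.875^10 = 74% at v = 0.3, and 1 − 0.9545^10 = 37% at v = 0.1.
- For m = 2 (the participant ceiling, at one event each): 1 − 0.700² = 51%, 1 − 0.875² = 23%, and 1 − 0.9545² = 9%.

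Unequal collection lowers the chance of seeing a contradiction but does not remove it. With only two events, even equal ascertainment gives about an even chance, so sparse data are a separate limit.

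**The case against.** The strongest case on the other side has five parts.

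- **The sentence is an expectation.** No test, threshold or decision hangs on it. A reader might infer that the profile match is one of the acceptability criteria, but the plan states those separately and this is not among them. This stands.
- **The expectation can fail.** A reader might infer that the collection method all but guarantees a match. It does not: spontaneous reports of any kind are recorded at every session, and one volunteered off-profile event would contradict the statement. Step 3 bears this out. This stands, and it limits the point to bias and a weak test.
- **Other sources exist.** Exit interviews, a treatment satisfaction form, and scales for mood, anxiety, sleep and function could bring out an unlisted problem. But the plan does not describe any of them as adverse-event capture, and none is an open question at each session. This stands in part.
- **The size is unsupported, and the prompt list may not equal the known profile.** Both are true. The documents show neither the full query nor the profile, so the line between known and off-profile cannot be drawn from the text. The direction of the bias needs only that the query targets TBS-associated effects, which is stated.
- **Little between-arm power is lost.** The plan specifies no between-arm adverse-event test, and 55 participants could show little about a rare event however it is collected. A reader might infer that a real iTBS–sham difference would be missed because of the query; the documents do not support so specific a claim.

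The eligibility section's remark that TBS is new in this population should not be pressed either, since it is given there as a reason for MRI-type safety screening.

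**Conclusion.** The point holds as a modest weakness in data collection. The adverse-event procedure favours known effects, so agreement between recorded events and the known TBS profile would be weak evidence that the profile carries over to PTSD. The direction rests on the text together with one ordinary assumption: that people report more of what they are asked about than of what they are not. The size cannot be established. On the assumptions above, a true known share of 70% would be recorded as anything from 70% to 95%. No stated threshold and no primary efficacy analysis is affected.

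The targeted query pulls the other way on the first half of the sentence: asking daily about effects such as headache tends to raise the count against the ceiling of 2 of 55. That does not correct the imbalance in the kinds of event recorded.

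**What to change.** In Participant Safety, have staff ask one open, non-leading question about any change in health before the TBS side-effect list, at every session and in identical words in both arms. Flag each event as open-question, volunteered or prompted.

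In Feasibility and Acceptability, report events by source and by arm for the blinded sessions. State in advance which effects make up the known profile. Base any statement about matching it mainly on the open-question and volunteered events, and note that answers after the first session may be primed by the list participants have already heard.

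The cost is one question in an existing daily contact, one field on the adverse-event form and a few lines of analysis text, with no added visit or staff. The downside is somewhat more recorded events in both arms, which makes the expectation of fewer than 5% harder to meet.

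### Mild TBI and sex are urn factors but not named covariates: a modest precision point for the end-of-treatment and 1-month comparisons

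*Combined protocol and SAP*

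**What the plan says.** All references are to the combined protocol and SAP.

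- **Randomization** (Procedures and Symptom Measures): urn allocation "with PTSD symptom severity, mild TBI, sex, and depression diagnosis (yes/no) as blocking variables".
- **Covariates** (DATA ANALYSIS, Data Analysis for RCT): variables fixed in advance that are "plausibly important for explaining the outcome (i.e., baseline PTSD, depression symptom severity and quality of life) and potentially differentially distributed by random assignment". The same paragraph opens by checking how the arms compare at baseline.
- **End-of-treatment test** (DATA ANALYSIS): the iTBS arm "will demonstrate greater change on outcome variables immediately after treatment completion compared to participants randomized to sham". Then: "This analysis focuses on end-of-treatment group (iTBS vs. sham) differences only, controlling for baseline differences".
- **1-month test** (DATA ANALYSIS): sustained change in "primary outcome measures at 1-month follow-up in the iTBS group as compared to the sham group, again net of any baseline differences".

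Of the four urn factors, baseline PTSD is a named covariate and depression enters as a severity score. Mild TBI and sex are not named. The references to baseline differences in the two tests name no variable.

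**The concern.** The usual principle is to analyse by the factors used to randomize. A factor that is balanced by design but left out of the model leaves its share of outcome variance in the error term. If mild TBI and sex predict outcome beyond the named covariates, the treatment estimate is less precise than it could be, and any imbalance the urn leaves goes uncorrected.

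There is also a question of discretion. The covariate list is introduced as complete, but the clause about differential distribution, placed after a balance check, could be read as letting further variables in or out once the data are seen. Naming the urn factors closes that off.

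Only the two comparisons at a single visit, adjusted for baseline, are at stake.

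**Working it through.** **Inputs from the document.** The planned size is "55 adult Veterans, ages 18-70 with current PTSD will participate in study procedures". For a smaller assessed sample, the feasibility criterion is "completion of a minimum of 75% of end of treatment and 1-month follow up assessments to reflect feasibility"; 0.75 × 55 = 41.25, so about 41. That is a minimum, not an attrition forecast. No power, alpha, effect size or SD is stated, so there is no planned figure to reproduce.

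**Assumed inputs.** Two-sided 0.05; effect 0.7 SD; baseline-outcome correlation 0.5; prevalence 0.40 for mild TBI and 0.15 for the less common sex; equal contributions of the two factors; the same factor effect at baseline and follow-up; dropout at random; a continuous outcome in a linear model at one visit.

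**Step 1: how much residual variance the factors can remove.** Write Y0 = F + U0 and Y1 = F + U1 + effect, total variance 1, var(F) = m.

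- Residual variance given baseline only: 1 − 0.5² = 0.75.
- Residual variance given baseline and F: (0.75 − m)/(1 − m).
- Residual R² = 1 − (0.75 − m)/[0.75(1 − m)] = m/[3(1 − m)].

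For m = 10%: 0.10/2.70 = 0.037. For m = 37.5%: 0.375/1.875 = 0.20. Baseline PTSD already carries much of a constant factor effect, which is why R² is well below m.

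**Step 2: standard error and power.** Simulation with 80,000 replicates per setting used an urn on the four factors, with balls summed over each patient's urns. It compared arm + baseline PTSD + depression severity + quality of life with the same model plus mild TBI and sex. Monte Carlo SE of the power differences is 0.07-0.13 points. In the assumed scenario the plan's covariates give 81.2-81.6% power at N = 55 and 67.0-67.6% at 41.

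| m | R² | SE, plan ÷ two-factor model (N = 55) | Power change, N = 55 | Power change, 41 assessed |
|---|---|---|---|---|
| 0% | 0 | 0.984 | −1.29 | −2.15 |
| 5% | 0.018 | 0.993 | −0.80 | −1.42 |
| 10% | 0.037 | 1.003 | 0.00 | −0.79 |
| 13% | 0.05 | 1.010 | +0.35 | −0.20 |
| 23% | 0.10 | 1.037 | +2.54 | +2.20 |
| 37.5% | 0.20 | 1.100 | +6.40 | +7.17 |

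The SE column can be checked by hand as 0.984/√(1 − R²): 0.984/√0.963 = 1.003 and 0.984/√0.80 = 1.100. Break-even is m of about 10% at N = 55 and about 14% at 41.

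**Step 3: what those shares mean.** With equal contributions, the difference between levels of a factor is √[(m/2)/(p(1 − p))].

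- m = 10%: √(0.05/0.24) = 0.46 SD for mild TBI and √(0.05/0.1275) = 0.63 SD for sex.
- m = 23%: √(0.115/0.24) = 0.69 SD and √(0.115/0.1275) = 0.95 SD.

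**Step 4: validity of the plan's own test.** The SE ratio above measures efficiency. Conservatism needs the plan's reported SE set against the estimate's actual sampling SD. That ratio is 0.997 at m = 5%, 0.998 at 10% and 1.004 at 37.5% (40,000 replicates), with type I error 5.0%, 5.1% and 4.7%. A separate 8,000-replicate run gave ratios of 0.99-1.01 and type I error of 5.0-5.3%. The 80,000-replicate runs at R² = 0.20 gave 4.8% or 4.3%, depending on how the urns are combined. Bias was at most 0.0015 SD.

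**Step 5: change contrast.** With baseline as a response, Y1 − Y0 = U1 − U0 + effect, so F cancels. Random-intercept models on three simulated 55-patient, three-visit data sets gave the same arm-by-visit estimates (6 decimals) and standard errors (within 0.000001) with and without the two factors as main effects.

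**Step 6: adding depression diagnosis too.** If none of the three is prognostic, this costs 1.97 points at N = 55 and 3.52 at 41. Break-even rises to about 15% and 20%.

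**The case against.** A reader might infer that leaving out urn factors makes the reported standard errors too large and the tests conservative. With exact balance that would follow. At 0.5 residual SD per factor and prevalences 0.20 and 0.30, error variance rises by 1 + 0.25 × (0.16 + 0.21) = 1.09 and actual alpha is 0.041. But an urn at N = 55 balances only partly; the mean absolute arm difference in the sex proportion is about 0.06 in simulation. Simulated type I error at that strength is 4.4-4.9%. It falls to 3.5-3.9% only with 0.8-1.0 residual SD for each factor (3,000 replicates, Monte Carlo SE about 0.4 points). The documents suggest no effects of that strength, so the conservative reading is not supported.

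A reader might also infer that the model ignores the randomization factors. It does not: baseline PTSD is named, and depression severity largely stands in for diagnosis.

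The strongest objection is that adding the two factors loses power below the break-even, and no passage suggests they are strong predictors. Importance for outcome is also a legitimate rule for choosing covariates in advance. This stands, and it limits the point to a minor one. It does not remove it. The loss is small and bounded, the team itself chose these factors as worth balancing, and fixing the list takes balance-driven choice out of the analysis.

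It also stands that the first hypothesis, on speed of improvement, is unaffected under a constant factor effect. The same holds for the other two if change is estimated with baseline as a response. Finally, the figures come from a single-visit linear model, whereas a repeated-measures GLMM is planned.

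**Conclusion.** The point holds as a cheap, minor improvement. Two of four urn factors are missing from the named covariates. The planned tests remain valid: no bias, no type I inflation, and type I error essentially nominal unless both factors are very strong. What can be gained is precision in two baseline-adjusted comparisons, correction of leftover imbalance, and a covariate list that does not depend on observed balance.

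Under the assumptions above, the change in power runs from about −1.3 points (−2.2 with 41 assessed) when the factors carry no information to between +2 and +7 points when they explain 23-37.5% of outcome variance. The upper end needs strong factors, or factors that act on change, and no passage indicates either. The direction is not sensitive to two of the choices. With an effect of 0.5 SD the change at N = 55 runs from −1.52 to +7.89 points; drawing from the most imbalanced urn gives −0.99 to +6.07 (40,000 replicates).

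**What to change.** In Data Analysis for RCT, add one sentence: mild TBI and sex enter the end-of-treatment and 1-month comparisons as pre-specified covariates, whatever balance is observed, and depression symptom severity stands in for depression diagnosis.

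The cost is that sentence and two degrees of freedom (55 − 5 = 50 error degrees of freedom become 48 in the single-visit model). Both factors are known at randomization, so no new data are needed. Keeping the severity score instead of adding the diagnosis as well avoids the third degree of freedom. If the team expects the two factors to explain less than about 10% of outcome variance (14% if only 41 are assessed), leaving them out is defensible, provided the plan says so in advance.

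### Four unranked scales are called primary and tested at more than one contrast, with no lead test, alpha or success rule for efficacy, so the plan does not control the false-positive rate of an efficacy claim

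*Combined protocol and SAP*

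**What the plan says.** The last part of Data Analysis for RCT names a method: "We will use generalized linear mixed models (GLMM) for repeated measures as our primary analysis". It then sets out three comparisons of iTBS with sham:

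- **Rate.** Faster improvement under iTBS "in primary outcomes, i.e. decreased CAPS/PCL and increased QLESQ/SOFAS".
- **End of treatment.** A test for "greater change on outcome variables immediately after treatment completion compared to participants randomized to sham", adjusted for baseline. Here the text refers to outcome variables in general and does not use the word primary.
- **One month.** Sustained change "in primary outcome measures at 1-month follow-up in the iTBS group as compared to the sham group", again net of baseline.

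A fourth analysis relates symptom change to change in quality of life and function. An open list of secondary outcomes follows.

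The only numeric success criteria in the document are under Feasibility and Acceptability. For acceptability the plan says: "We will consider 75% session attendance and satisfaction rates of 70% participants as the minimum indicator of acceptability". For feasibility the threshold is likewise 75%, applied to the share of scheduled post-treatment assessments that are completed. No section gives an alpha, a sidedness, a multiplicity adjustment, a ranking of the four scales, or an any-one or all-four rule for efficacy. Efficacy is not described as exploratory either.

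**The concern.** A mixed model is a method. It becomes a primary test only when it is tied to one scale, one contrast and one significance level, and the plan does not make that link. Four scales carry the primary label, and at least two contrasts (rate and 1 month) are attached to it. The words that introduce the later tests (next, third, finally) give an order of presentation; no test depends on the result of an earlier one.

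An analyst who followed the plan exactly could therefore hold several primary p-values and put any of them forward as the main result. A reader could not tell a planned main finding from one picked after the data were seen. With 55 participants and no stated power basis, that distinction largely decides how a positive result can be read.

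**Working it through.** The plan states no error rate, so there is no figure to reproduce. The check asks what the rate would be under each success rule that the text leaves open.

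**Inputs from the document.** 55 participants; four primary scales; three iTBS-versus-sham contrasts; 75% assessment completion accepted as feasible.

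**Assumed, because not stated.** Two-sided 0.05 per test; 1:1 allocation (28/27); normal data; between-scale correlation 0.3 to 0.9; correlation over time 0.5 or 0.7. End-of-treatment and 1-month tests are by ANCOVA on baseline. Rate is tested as pre-post change or as a linear slope over assumed weeks 0, 2 and 6.

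**Direction.** The hypotheses are directional, and a result favouring sham is not a false claim of efficacy. The relevant benchmark for one test is therefore 0.05 / 2 = 2.5%.

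**Step 1: any one of four scales, one contrast.**
- If the tests were independent: 1 − (1 − 0.025)^4 = 1 − 0.975^4 = 9.6%.
- With correlated scales, simulated under no effect (60,000 trials per setting, end of treatment): 4.5% to 8.9%. The low end belongs to correlation 0.9 and the high end to 0.3.
- With a random-intercept mixed model and a quarter of post-baseline assessments missing at random: 4.0% to 9.7%.

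**Step 2: any one of four scales on any of three contrasts.**
- If independent: 1 − 0.975^12 = 26.2%.
- Simulated with the correlations above: 10.0% to 19.3%. Mixed model with missing data: 9.4% to 19.8%.
- This result is sensitive to the assumed correlations. A calculation with correlations of 0.3 to 0.7 both between scales and between contrasts gives 13% to 22%.

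**Step 3: all four scales must succeed, one contrast.**
- iTBS affects none of them: about 1% or less favouring iTBS.
- iTBS truly affects three scales (by 1.2 SD) and not the fourth: 2.4% to 2.6%. The three real effects are nearly always detected, so the error is simply that of the one remaining test.

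| Success rule (not stated in the plan) | Chance of a false result favouring iTBS |
|---|---|
| One named test | 2.5% |
| All four scales, one contrast | about 1% or less if no scale is affected; 2.5% if three are |
| Any of four scales, one contrast | about 5% to 9% |
| Any of four scales, three contrasts | about 10% to 19% |

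**Step 4: does a fixed order repair it?** Four scales at one contrast were tested in a set order, each at two-sided 0.05 and only if the one before was significant. With none, the first, the first two or the first three scales truly affected, the familywise error in both directions was 4.7% to 5.2%, which is 5% within simulation error.

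**The case against.** Three arguments on the other side deserve weight.

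**A lead can be read from the text.** The repeated-measures model is called primary and the rate test comes first. A rate test spans the visits and needs no lead time point. This stands in part, because the rate test is a legitimate candidate for lead. But it still covers four unranked scales, has no alpha and gates nothing.

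**The larger percentages depend on a family that the reader builds.** This stands. The primary label is attached to the rate and 1-month tests, while the end-of-treatment test is on unspecified outcome variables. Nothing says that any of 12 tests would suffice. The four-scale figures are the better supported, and the 12-test range is only an indication of how far the error could go.

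**This may be a feasibility trial.** Feasibility and acceptability come first and have the only numeric criteria, and no power statement is made. That is a fair reading, and if it is the intended one a single sentence settles the matter. As written, however, the efficacy section speaks of a primary analysis and of testing hypotheses.

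A reader might go further and infer that the plan lets any one significant result count, so that its error rate is a known inflated value. The document does not support that, since it states neither an any-one nor an all-four rule. It would also be wrong to call the all-four rule safe at 1% without qualification, because that figure holds only when iTBS affects none of the scales.

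**Conclusion.** The concern holds in limited form. Four scales are primary without ranking, more than one contrast is tested on them, and no alpha, lead test, testing order or success rule is given for efficacy. The error rate of an efficacy claim is undefined; the plan does not commit to any particular inflated value.

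The best-supported illustration is any one of four scales at one contrast: roughly two to three and a half times the one-test rate (4.5 / 2.5 = 1.8; 8.9 / 2.5 = 3.6). All the percentages rest on the assumed alpha, allocation and correlations, none of which the document states. The finding of no control rests on the text alone. The plan should be amended on this point, although the remedy is small.

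**What to change.** Before any unblinded efficacy analysis, name one primary test: one scale, one contrast, with its alpha and sidedness. Test the other three scales on the same contrast in one fixed order, each only if the previous one is significant. Report the remaining contrasts as secondary, with estimates and confidence intervals.

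Adjust each scale for its own baseline value along with the planned covariates. The listed set, "baseline PTSD, depression symptom severity and quality of life", does not include baseline SOFAS and does not say whether baseline PTSD means CAPS-5 or PCL-5.

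The choice of lead is the sponsor's. Two candidates have support in the text:

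- **CAPS-5 at the end of the double-blind phase.** CAPS-5 is the scale that "will be used to establish a PTSD diagnosis at baseline", and this time point precedes the unblinded sessions offered afterwards, which could affect the 1-month comparison. This choice promotes the one between-group test that the plan does not attach to primary outcomes, and it demotes the two that it does. The sponsor should say so openly.
- **The rate test on one named scale**, which the plan lists first.

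If the trial is meant as a feasibility study, an equally acceptable route is to state that all efficacy tests are exploratory and make no confirmatory claim.

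**Cost.** The change is wording only, with no added patients or visits. Scales and contrasts other than the lead can no longer each support a stand-alone primary claim, and a scale placed after a failed one cannot be claimed. Full alpha stays on the lead test. For an end-of-treatment lead, the detectable difference at 80% power and two-sided 0.05 (assumed baseline correlation 0.7 to 0.5) is 0.55 to 0.67 SD if all 55 complete. It is 0.64 to 0.78 SD at 75% completion (0.75 × 55 ≈ 41 patients). Splitting alpha equally over four scales (0.05 / 4 = 0.0125) would raise these to 0.66 to 0.80 SD and 0.78 to 0.94 SD, which is why a fixed order is preferable in a trial of this size.
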